6.1. Study Objectives

The primary objective of this study is to collect real-world outcomes data on the WATCHMAN FLX Pro Left Atrial Appendage Closure (LAAC) Device in patients who are implanted with the WATCHMAN FLX Pro device in a commercial clinical setting.

6.2. Study Endpoints

Outcomes in HEAL-LAA will be assessed on an intention-to-treat (ITT) basis and an implanted basis. The ITT analysis set includes all subjects who sign an Informed Consent Form approved by the Institutional Review Board (IRB), meet all clinical inclusion and no clinical exclusion criteria, and the WATCHMAN FLX Pro device has been used for treatment and/or attempted to be used for treatment. The implanted analysis set includes ITT subjects who are implanted with the study device in the correct anatomical position (see full definitions within **Table 9-1** and **Table 24-2**).

The trial endpoints are listed below. Measurements will be collected at baseline, pre-implant on the procedure day through discharge, and at 45 days, 6 months, and 12 months after the implant procedure, unless specified otherwise.

The **primary efficacy endpoint** is: The rate of leak >5 mm at 45-day post-implant TEE for the WATCHMAN FLX™ Pro Primary Analysis Subset is less than a performance goal (PG).

The **primary safety endpoint** is: For the evaluable cohort, the composite rate of all-cause mortality, all stroke, systemic embolism, and major bleeding at 6 months for the WATCHMAN FLX™ Pro Primary Analysis Subset is less than a performance goal (PG).

The Primary Analysis Subset consists of data from the initial 500 enrolled subjects.

Additional endpoints will include the following:

The individual components of the composite safety endpoints above will be reported separately in addition to the overall composites.

The following will also be analyzed:

- Death: Cardiovascular/unknown death and non-cardiovascular death
- Stroke: Disabling and non-disabling stroke; ischemic and hemorrhagic stroke
- Bleeding: International Society on Thrombosis and Haemostasis (ISTH) major and non-major clinically significant
 - Procedural bleeding (≤ 7 days post-procedure)
 - Non-procedural bleeding (>7 days post-procedure)

- Device related thrombus
- Pericardial effusion/tamponade requiring pericardiocentesis or surgery to treat
- Device implant success

See full definitions within **Table 24-2**.

Subset Analysis will be analysed per Section **11.3.4**.

7. Study Design

HEAL-LAA is a prospective, post-market, single-arm, multi-center trial evaluating safety and device success of the WATCHMAN FLX Pro closure device in subjects with non-valvular atrial fibrillation (AF).

[figure not shown]
7.1. Scale and Duration

Approximately 1000 subjects at up to 60 investigational centers in the United States will be enrolled in HEAL-LAA. Eligibility for the study is determined per standard of care. Any study specific testing to verify inclusion/exclusion criteria that is not considered Standard of Care at a given investigational center must be assessed after the ICF is signed. A patient is considered enrolled once an informed consent form has been signed, all clinical inclusion and no clinical exclusion criteria have been met, and the WATCHMAN FLX Pro device has been used for treatment and/or attempted to be used for treatment.

A subject who signs an ICF but does not meet clinical eligibility criteria and/or is not treated or attempted to be treated with a WATCHMAN FLX Pro device is considered a screen failure. Screen failure subjects should exit from the study immediately upon determining ineligibility.

Subjects who are enrolled but the attempted treatment with a WATCHMAN FLX Pro device was not successful will be followed for safety through 12 months after the initial attempted index procedure but will not undergo imaging assessments. See full "Attempted" definition within **Table 9-1**.

All subjects will be assessed at baseline and pre-implant on the procedure day through discharge, and at 45 days, 6 months, and 12 months post index procedure. Follow-up will include in-person clinical assessments at all time points except 6 months (in person [preferred] or by telephone). Follow-up imaging assessments will occur at 45 days and 12 months. Additional imaging may be done at 6 months per institution standard imaging practice.

[^] Subjects must sign the study ICF before any Non-Standard of Care / study-specific assessments can be carried out. If all baseline and procedure assessments are SOC, subject may sign after receiving the WATCHMAN FLX Pro device.

[‡] Visits are in-person at 45 days & 12 months and in-person (preferred) or via telephone interview at 6 months.

Figure 7.1-1: HEAL-LAA Study Design

Enrollment is expected to take 6 months. Therefore, the total study duration from first subject enrolled to last subject follow-up is estimated to be at least 18 months. The study duration for each subject is expected to be approximately 12 months.

The HEAL-LAA study will be registered at www.ClinicalTrials.gov prior to enrollment of the first subject (see Section 21.1).

7.2. Treatment Assignment

HEAL-LAA is a post-market study. All subjects who meet all inclusion criteria and no exclusion criteria can be enrolled. A subject is considered enrolled in the study when the subject signs an ICF approved by the IRB, meet all inclusion criteria and no exclusion criteria, and are treated with or attempted to be treated with a WATCHMAN FLX Pro device. See Section 5.1 for a detailed description of the device and information on device sizes.

Additional patient subsets and/or analyses of interest may be included in the trial. An Enrollment Guide(s) will be provided to sites in order to communicate which patient subsets are eligible for enrollment and which subsets are no longer eligible for enrollment.

Subjects may meet more than one subset requirement and therefore may have their data analyzed in multiple subsets. Requirements for each subset will be outlined in the Enrollment Guide. Additional eligibility criteria outside of those listed within this protocol (Sections 8.2 and 8.3) will not be introduced within the Enrollment Guide.

7.3. Justification for the Study Design

HEAL-LAA is an observational, post-market study designed to collect real world data on the WATCHMAN FLX Pro LAAC device to support further regulatory submissions. Device implantation will be done according to current indications and device labelling as described in the device IFU. Safety results and device success will be reported on all enrolled subjects. Enrolled subjects will be followed for up to 12 months post index procedure.

8. Subject Selection

8.1. *Study Population and Eligibility*

The intended population for the HEAL-LAA trial is real-world patients who are treated with the commercially available WATCHMAN FLX Pro device. Efforts will be made to include study centers with diverse patient populations in order to enroll populations previously not represented in LAAC trials.

Eligibility for this study is determined per standard of care. Any subject who meets all the inclusion criteria, does not meet any of the exclusion criteria, and who provides written informed consent may be considered for enrollment in the study (see **Note 1** below). The subjects selected for participation may be from the Investigator's general patient population. The investigator has the responsibility for screening all potential subjects and selecting those who meet study inclusion criteria and do not meet any of the exclusion criteria as described below. All subjects will have unique identification numbers.

Note 1: Vulnerable subjects (see **Table 24-2** for the definition of vulnerable subject) will not be enrolled in the HEAL-LAA study.

8.2. *Inclusion Criteria*

Subjects who meet all of the following criteria (see **Table 8-1**) may be given consideration for inclusion in this clinical investigation, provided no exclusion criterion (see Section **8.3**) is met.

Table 8-1: Inclusion Criteria

Inclusion Criteria	
IC1. Subject is of legal age to participate in the study.
 
IC2. Subject has documented non-valvular atrial fibrillation (i.e., atrial fibrillation in the absence of moderate or greater mitral stenosis or a mechanical heart valve).
 
IC3. Subject is clinically indicated for and is treated or attempted to be treated with a WATCHMAN FLX™ Pro device.
 
IC4. Subject or legal representative is able to understand and willing to provide written informed consent to participate in the study.
 
IC5. Subject is able and willing to return for required follow-up visits and examinations.

---------------------------	---

Abbreviation: IC=inclusion criterion

8.3. *Exclusion Criteria*

Subjects who meet any one of the following criteria (see **Table 8-2**) will be excluded from this clinical study. No vulnerable populations will be enrolled in this study.

Table 8-2: Exclusion Criteria

Exclusion Criteria	
EC1. Subject has a documented life expectancy of less than 6 months.
 
EC2. Subject is currently enrolled in another investigational study, except if the subject is participating in a mandatory governmental registry, or a purely observational registry with no associated treatment.
 
EC3. Intracardiac thrombus is present.
 
EC4. An atrial septal defect repair or closure device or a patent foramen ovale repair or closure device is present.
 
EC5. The LAA anatomy will not accommodate a Closure Device.
 
EC6. The patient has known hypersensitivity to any portion of the device material or the individual components such that the use of the WATCHMAN FLX™ Pro Device is contraindicated.
 
EC7. Any of the customary contraindications for other percutaneous catheterization procedure (e.g., patient size too small to accommodate TEE probe or required catheters) or conditions (e.g., active infection, bleeding disorder) are present.
 
EC8. There are contraindications to the use of anticoagulation therapy, aspirin, or P2Y₁₂ inhibitor.
 
EC9. Subject is of childbearing potential and is, or plans to become, pregnant during the time of the study (method of assessment per study physician's discretion).

---------------------------	--

Abbreviations: EC=Exclusion Criteria; LAA=left atrial appendage; TEE=transesophageal echocardiography

9. Subject Accountability

9.1. *Point of Enrollment*

Subjects are considered enrolled in the study when the subject signs an ICF approved by the IRB, all clinical inclusion and no clinical exclusion criteria have been met, and the WATCHMAN FLX Pro device has been used for treatment and/or attempted to be used for treatment. Both Attempt and Implant subjects as defined in **Table 9-1** are considered enrolled subjects. A subject who is determined to not meet study specific clinical eligibility criteria after signing consent will be considered a screen failure (see **Table 9-1**) and will not count towards the enrollment ceiling.

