9.4. Subject Status and Classification

Table 9-1 describes subject status/classification and associated forms.

Table 9-1: Subject Status and Classification

Classification	Description
Screen Failure	A subject who signs an ICF but does not meet clinical eligibility criteria and/or is not treated or attempted to be treated with a WATCHMAN FLX Pro device is considered a screen failure. Screen failure subjects do not count towards the enrollment ceiling and will not be used for the primary analyses. Screen failure subjects should exit from the study immediately upon determining ineligibility. The original signed ICF must be maintained in the center's subject file.
Attempt	A subject who signs an ICF, meets eligibility criteria, and has had a WATCHMAN Access Sheath inserted to implant the device, but does not receive a WATCHMAN FLX Pro device will be classified as "Attempt." Subjects in which a WATCHMAN FLX Pro device is inserted into a different anatomical location/structure (not within the LAA) will also be classified as "Attempt." Attempt subjects will be followed for 12 months from the time of the implant attempt and adverse events will be collected. Attempt subjects will not undergo protocol required imaging at 45 days or 12 months. Attempt subjects are considered enrolled and therefore count towards the enrollment ceiling. Attempt subjects will be used for analyses of the ITT analyzed endpoints. The original signed ICF must be maintained in the center's study file and the following forms must be completed. 
 • eCRFs in the Baseline and Implant folders • Follow-up Visit Form(s), except LAA imaging • Adverse Event forms and/or Device Deficiency forms for any reportable adverse event that occurs after signing the ICF • End of Study form for withdrawal The date of withdrawal should be indicated in the End of Study form as the point of subject withdrawal.
Implant	A subject who signs an ICF, meets eligibility criteria, and is implanted with the WATCHMAN FLX Pro device will be classified as "Implant." Implanted subjects are those where the device has been deployed and implanted in the correct anatomical position (LAA). These enrolled subjects are followed in accordance with the follow-up schedule and data will be included in all study analyses. All applicable case report forms per the protocol must be completed. The original signed ICF and any relevant documentation must be maintained in the center's study file.

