10.3. Informed Consent

Subjects must sign the approved study ICF before any non-standard of care, study specific assessment can be assessed. If all baseline and procedure assessment/procedures are SOC, a subject may sign the ICF after receiving the WATCHMAN FLX Pro device. Subjects that have signed and dated the ICF, have met all clinical inclusion and no clinical exclusion criteria, and have been treated with or attempted to be treated with a WATCHMAN FLX Pro device are considered enrolled in the study. The original, signed document is to be kept with the subject's file and a copy must be provided to the subject. The informed consent process must be documented by the person obtaining consent and the documentation must be placed in the subject's file.

The Investigator/designee who has been trained on the protocol will explain the nature and scope of the study, the potential risks and benefits of participation, and will answer questions for the subject. Patients must be given ample time to review the ICF and have questions answered before signing.

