4 GENERAL STATISTICAL METHODS

4.1 Subject Status and Classification

4.1.1 Screen Failure

A subject who signs an ICF but does not meet clinical eligibility criteria and/or is not treated or attempted to be treated with a WATCHMAN FLX Pro device is considered a screen failure. These subjects do not count towards the enrollment ceiling and will not be used for any planned endpoint analyses.

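### Screen-failure status has no cut-off at sheath insertion or implant, so a treated subject can leave the ITT set and safety follow-up, and the Attempt, EC5 and TruSteer definitions conflict

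*Protocol*

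**What the plan says.** **Screen failure.** Protocol Section 9.1: "A subject who is determined to not meet study specific clinical eligibility criteria after signing consent will be considered a screen failure". Section 7.1 and Table 9-1 define the class in nearly the same words; Table 9-1 has "A subject who signs an ICF but does not meet clinical eligibility criteria and/or is not treated or attempted to be treated". The and/or means that ineligibility alone is enough, whether or not the subject was treated.

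**Consequences.** Table 9-1: "Screen failure subjects should exit from the study immediately upon determining ineligibility". SAP 4.1.1: "These subjects do not count towards the enrollment ceiling and will not be used for any planned endpoint analyses". Section 17.1 limits event reporting to enrolled subjects.

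**Attempt.** Table 9-1 describes "A subject who signs an ICF, meets eligibility criteria, and has had a WATCHMAN Access Sheath inserted to implant the device" but who does not receive it. Attempt subjects count as enrolled, are followed for 12 months and are used in ITT analyses. SAP 4.1.2 keeps the eligibility condition. Implant (Table 9-1, SAP 4.1.3) and ITT (Protocol 11.2.1, SAP 4.2) require eligibility too.

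**EC5 (Table 8-2).** "The LAA anatomy will not accommodate a Closure Device".

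**Consent (Section 10.3).** When all baseline and procedural assessments are standard of care, "a subject may sign the ICF after receiving the WATCHMAN FLX Pro device".

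**TruSteer.** SAP 4.1.4 defines TruSteer Attempt without any eligibility condition and places these subjects in the Access System Subset analyses. SAP 3.3.3 restricts the denominator to enrolled subjects.

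**The concern.** An ITT set should not lose subjects after treatment on grounds that can be linked to the outcome. Here the rule that removes subjects stays open after the procedure. On the consent-after-implant pathway, any ruling made after consent is necessarily made after treatment.

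EC5 is the sharpest case. An anatomy that will not take the device is both an exclusion criterion and a natural explanation for a failed implant. Two sites following the text could classify the same sheath-in, no-device subject in opposite ways: one as Attempt, followed for 12 months and analysed, the other as a screen failure who exits.

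Two results are exposed. The first is the primary safety composite, analysed on ITT, which would lose any death, stroke, systemic embolism or major bleed in a removed subject. The second is implant success, including the hypothesis test in the Access System Subset, where a removed failure leaves the denominator and can be replaced, because screen failures do not count toward enrolment. The removed subjects would also lose protocol safety follow-up, and data not collected after an early exit may not be recoverable. Failed implants do not affect the leak endpoint, which uses the implanted set; removal of implanted but ineligible subjects could.

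**Working it through.** **1. Is there a cut-off?** Set side by side:

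- Section 9.1 is triggered by ineligibility found after consent, with no end point.
- Section 7.1 and Table 9-1 need only ineligibility, so a treated subject is not protected.
- Section 10.4 lists confirmation of eligibility among the pre-procedure data, to be collected within 30 days before the procedure. The item lacks the star that marks what is expected before implant, and Section 10.3 allows consent after implant. It points to screening before the procedure but does not lock it.
- SAP 4.2, 3.3.3 and 7.2 retain subjects who are enrolled. Enrolment itself requires eligibility (Sections 7.1 and 9.1), so these sections do not bring back a subject ruled ineligible.

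No cut-off is stated.

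**2. The plan's own figures.** The formula is power = Φ[(|p0 − p1| − 1.96·√(p0(1−p0)/n)) / √(p1(1−p1)/n)].

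- Access System Subset (SAP 3.3.2; n = 300, p0 = 0.94, p1 = 0.978): (0.038 − 1.96 × 0.01371)/0.00847 gives 90.5%, consistent with the stated figure above 90%.
- Safety (Protocol 11.1.2.2; n = 485, p0 = 0.21, p1 = 0.14): 98.4%, consistent with the stated figure above 95%. Also 485/(1 − 0.03) = 500.

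The planned sample sizes are not in question.

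**3. TruSteer illustration.** The critical value is 0.94 + 1.96·√(0.94 × 0.06/300) = 0.9669. With 10 failures the rate is 290/300 = 0.9667, which does not pass; with 9 it is 291/300 = 0.9700, which does. The test therefore passes with at most 9 failures.

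Let q be the true failure rate and f the fraction of failures relabelled as screen failures and replaced. The observed failure rate is q(1 − f)/(1 − qf). The chance of passing is P(X ≤ 9) for X binomial with n = 300 and that rate. The values of f are assumptions; the documents give none.

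| f | Observed failure, true success 94% | Chance of passing | Observed failure, true success 97.8% | Chance of passing |
|---|---|---|---|---|
| 0% | 6.00% | 1.3% | 2.20% | 87% |
| 10% | 5.43% | 3.4% | 1.98% | 92% |
| 25% | 4.57% | 11.8% | 1.66% | 97% |
| 50% | 3.09% | 55.0% | 1.11% | 99.8% |

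The 87% at f = 0 is the exact binomial counterpart of the 90.5% in step 2; the difference comes from the whole-number cut-off.

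**4. Safety illustration.** The cut-off is 0.21 − 1.96·√(0.21 × 0.79/485) = 0.1738, and 0.1738 × 485 = 84.3, so the test passes with at most 84 events. Suppose a share s of treated subjects, with an assumed event rate of 50%, is removed and the evaluable number stays at 485. The observed rate is (0.21 − 0.5s)/(1 − s). At a true rate of 21%, the chance of passing is 2.5% for s = 0, 4.9% for s = 2% (observed 20.4%) and 12.6% for s = 5% (observed 19.5%). Both s and the 50% are assumptions.

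**The case against.** The best reply is that failed implants already have their own class. Table 9-1 defines the subject who "has had a WATCHMAN Access Sheath inserted to implant the device, but does not receive a WATCHMAN FLX Pro device will be classified as" Attempt. Section 7.1 follows unsuccessful attempts for 12 months, Section 9.1 counts Attempt and Implant subjects as enrolled immediately before the screen-failure sentence, and SAP 4.1.2 puts Attempts into the ITT analyses. On a natural reading, the specific rule governs a sheath-in failure and the screen-failure rule governs screening. A device that will not seat is not in itself a finding of EC5. Section 10.4 supports this reading, and for the TruSteer test SAP 4.1.4 imposes no eligibility condition at all.

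Much of this stands. It shows the probable intent, and a careful site would classify as Attempt. It does not remove the conflict, because Attempt carries the eligibility condition and SAP 3.3.3 and 4.1.1 restrict analysis to subjects who are not screen failures.

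The reply also limits the size. A subject in whom TruSteer failed but another access system delivered the device counts as a TruSteer failure (SAP 4.1.4), and EC5 cannot remove that subject because the anatomy did take the device. This caps f for that test.

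A reader might infer three stronger things, none of which the documents support:

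- *That the plan routinely discards failed implants.* No section says that relabelling after the procedure is intended, and the Attempt class points the other way.
- *That anatomy or thrombus is commonly first judged late.* Pre-procedure imaging is optional but recommended, and procedural TEE or ICE is required; nothing says how often a ruling follows sheath insertion.
- *That tamponade as such leaves the safety composite.* It is an additional endpoint and enters the composite only if adjudicated as major bleeding.

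**Conclusion.** The point holds as a wording gap with consequences for the analysis sets. The stated rules permit a consented, treated subject to be removed from ITT and from safety follow-up. Attempt, EC5, TruSteer Attempt and the enrolled-only denominators give conflicting answers for the same subject and must be reconciled.

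The likely direction favours the device; the size is unknown. The pass probabilities above show sensitivity to an assumed relabelling fraction and do not estimate what will happen. Near the performance goal even a modest fraction matters: at a true 94%, the chance of passing goes from 1.3% to 11.8% at f = 25%. At the planned 97.8% the test would usually pass anyway (87% against 97%), so it should not be inferred that the TruSteer or safety conclusion depends on this gap. Severity: should be fixed, preferably before more subjects exit without follow-up.

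**What to change.** In Protocol 7.1, 9.1, Table 9-1 and 11.2.1, and in SAP 4.1.1 to 4.1.5 and 4.2, state that:

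- screen-failure status cannot be assigned once a WATCHMAN Access Sheath has been inserted to implant the device, including when consent is signed after the procedure;
- any such consented subject is Attempt or Implant (and TruSteer Attempt or TruSteer Implant where that applies), stays in ITT and is followed for safety to 12 months;
- ineligibility found later is recorded as a protocol deviation, and a sensitivity analysis excludes those subjects.

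The change concerns classification and analysis only. It should not prescribe when EC3 or EC5 is assessed clinically.

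Cost: a wording amendment to both documents, no new procedures, and sample sizes unchanged at 500 and 300. A few ineligible subjects will remain in ITT and be followed, so the set departs slightly from the intended population and rates may be slightly less favourable. The sensitivity analysis shows how much.
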